17.3.4. Utility measurement

For the purposes of cost-effectiveness analysis, quality of life must also be measured in terms of "utility", a global rating (on a 0-1 scale) that reflects an individual's preference for his or her current health state relative to perfect health.²⁹ Although in the past, it had been customary to measure utility directly from trial participants using time-tradeoff techniques,^{156,157} there is an emerging consensus that cost-effectiveness analyses designed to inform societal resource allocation use community-based (rather than subject-based) preferences.¹⁵⁸

There are a number of potential techniques for measurement of subject-specific, populationbased utility weights within the EXCEL trial. These include the Health Utilities Index (HUI),¹⁵⁹ the Quality of Well-Being Scale (QWB),¹⁶⁰ the EuroQol (EQ-5D),⁸³ and recently published algorithms that allow mapping of the SF-36 or SF-12 to health state utilities.^{161,162} Although each of these approaches has intrinsic advantages (and disadvantages), the preferred utility instrument for the EXCEL trial is the EQ-5D. The EQ-5D is a multiattribute health status classification system with an empirically-derived preference based scoring system based on analysis of time trade-off utilities for selected health states among 2997 randomly-selected members of the adult population of the U.K.¹⁶³Recently, analogous preference-weights have been developed for U.S. population utilities.⁸⁴ Although the EQ-5D was not specifically developed for use in subjects with coronary artery disease, it offers several specific advantages for this trial. First, it is based on a health state classification system that includes five specific domains of health: mobility, self-care, usual activities, pain/discomfort, and anxiety/depression. By incorporating many of the domains that are likely to be affected by coronary artery disease and its complications, such as pain, physical limitations, and role limitations, the EQ-5D should capture important differences in health within the study population. Second, the EQ-5D may be administered by either a five item written questionnaire or telephone interview and thus should add little burden to the overall data collection task. By comparison, both the HUI and the QWB questionnaires are substantially longer and, in previous experience, are often too burdensome for chronically-ill subjects. Finally, considerable practical experience with the EQ-5D exists as it has been used successfully as the principal utility measure in the Benestent II Trial $(n=823)^{164}$ and the PAMI Stent trial (n=900), ¹⁶⁵ and most recently in the SYNTAX trial.

17.3.5. Economic Data Collection

The following data elements will be obtained from the EXCEL trial database for use in this substudy:

- Measures of global medical resource utilization for each hospitalization including length of stay and number of ICU days.
- Cardiac catheterization laboratory resource utilization for the index procedure as well as any subsequent catheterizations or PCI procedures required during the follow-up period. Data collected will include total procedure duration; numbers of angioplasty balloons, stents (bare and drug-eluting), guidewires, ultrasound catheters, and guiding catheters used; adjunctive medications used including glycoprotein IIb/IIIa antagonists and direct thrombin inhibitors; and the amount and type of contrast dye required. These data will provide a direct measure of resource utilization for the two strategies, and will be used to examine the true costs of initial PCI based on standard, "bottom-up" accounting measures.^{85,166}
- Measures of global resource utilization for each initial and follow-up hospitalization for treatment of cardiovascular disease, its direct complications, and potential complications of treatment. For each hospital admission, these data will include total length of stay, number of ICU days, principal diagnosis, and major procedures performed during the hospitalization (e.g., coronary revascularization, pacemaker or ICD implantation, peripheralvascular surgery). Hospital admissions unrelated to treatment of cardiovascular disease or potential complications of its treatment will be identified by an independent review committee, blinded to initial treatment assignment and excluded from the economic analysis, since any differences in these events are unlikely to be related to the assigned treatment strategy. Thus, their inclusion in the economic analysis would only increase the variance of the cost estimates and reduce statistical power.
- Detailed listing of outpatient medications for treatment of cardiovascular disease at each follow-up subject contact.
- Subject estimates (by self-report) of utilization of outpatient cardiovascular services including diagnostic testing (e.g., ETT, nuclear stress testing, echocardiography, cardiac

CT); outpatient procedures (e.g., diagnostic catheterization, cardioversion); and physician visits.

• Number and duration of admissions to rehabilitation hospitals, nursing homes, and other chronic care facilities.

17.4. Cost Measurement

17.4.1. Procedural Costs

Catheterization laboratory and bypass costs will be calculated for each subject using standard, "bottom-up" cost accounting methods using the most current unit costs available at the time of each analysis.⁸⁵ For example, if the 1-year analysis is performed in 2013, every effort will be made to obtain updated unit costs for 2013. Similarly, if the 5-year analysis is performed in 2015, unit costs for that year will be used as the basis for the cost analysis. The rationale for using updated costs is that the goal of the cost-effectiveness analysis is to inform ongoing policy development and not merely to describe historically-relevant costs.

For major disposable items (including angioplasty balloons, bare metal and drug-eluting stents, guidewires, and guiding catheters), costs will be based on a survey of U.S. hospital and catheterization laboratory administrators as to the acquisition costs for the item at the time of the analysis. Drug costs for procedural anticoagulants including glycoprotein 2b/3a antagonists, direct thrombin inhibitors, and thrombolytic agents will be determined in a similar fashion. Updated cost data for the final calculations and analysis will ensure that the cost estimates are accurate at the time of publication. The cost of other disposables, depreciation, and overhead for catheterization laboratory maintenance, and non-physician personnel will be estimated based on the average cost per procedure at 3-5 geographically diverse U.S. medical centers during the same time frame and adjusted for measured procedure duration. Similar methods will be applied to estimate the procedural cost of CABG.

17.4.2. Non-procedural Hospitalization Costs

The non-procedural costs of hospitalizations will be estimated in two ways. The primary method will utilize an event-based approach to estimating costs; the secondary approach will utilize a resource-based approach. The advantage of the event-based approach to hospitalization costs is that it does not rely on an assumption of comparability of length of stay between U.S. and non-U.S. subjects. Rather, nationally-representative data will be used to estimate the cost of an uncomplicated hospital admission and also the relationship between specific procedural complications and hospital costs. This approach is identical to one that has recently been employed for calculation of costs in the SYNTAX trial. Details of this estimation process are outlined below.

The event-based approach relies on the Medicare Provider and Review (MedPAR) database. The MedPAR file is an administrative database maintained by the Centers for Medicare and Medicaid Services containing all claims submitted by hospitals for services provided to Medicare beneficiaries. For each hospitalization, the MedPAR record includes information on age, sex, race, date of admission, date of discharge; the principal diagnosis code (ICD-9-CM), eight secondary ICD-9-CM diagnosis codes, six ICD-9-CM procedure codes, discharge status, total

charges, total reimbursement, and the hospital's Medicare provider number.

Estimating costs consists of three steps. In the first step, the MedPAR database will be used to model the relationship between the total index hospitalization costs and the costs associated with various complications occurring after the procedure of interest but during the index hospitalization. Estimates of the costs of these complications will be obtained via a regression using a model with structure:

$$TC_{i} = A + X_{i}\beta + Z_{i}\delta + u_{i}$$

where TC_i is the total cost of the index hospitalization for subject i, X_i is a set of indicator variables for subject i denoting whether particular complications occurred, β is an associated parameter vector representing the estimated costs of the complications, Z_i is a set of individual baseline subject characteristics (e.g., age, sex, etc.), δ is an associated parameter vector representing the incremental cost of the characteristics, A represents the sum of procedural costs and any other costs for an uncomplicated hospitalization, and u_i is a residual. This model will be estimated separately for each procedure type.

The second step will be to obtain an estimate of the mean cost of uncomplicated hospitalizations. Letting UHC be uncomplicated hospitalization costs (excluding procedural costs), and PC be procedural costs, for each subject is defined as:

$$\overline{W} = \overline{UHC} + \overline{PC}.$$

 $W_i = UHC_i + PC_i$

Since the regression in step 1 does not specify a separate intercept for each subject, it is reasonable to think of A as an average across all subjects, i.e., that \hat{A} is an estimate of \overline{W} . Then a straightforward way to estimate mean uncomplicated hospital costs (*UHC*) is to subtract an estimate of mean procedure costs (\overline{PC}) from the estimate of A, i.e.,

$$\overrightarrow{UHC} = \overrightarrow{A} - \overrightarrow{PC}$$

Mean procedure costs for use in this step will be obtained from the REPLACE-2 trial (14) or a comparable multicenter registry or trial that reflects contemporary PCI practice in a broad, relatively unselected subject population.

The third step is to combine the previously obtained parameter values to produce an estimate of U.S.-relevant costs based on the data from the EXCEL trial. First, an estimate of subject-specific variable costs (Q_i) will be obtained by the estimates of β and δ (as previously derived from the MedPAR analyses) to the EXCEL subject data, i.e.,

$$\dot{Q}_{i} = X_{i}\beta + Z_{i}\delta,$$

where β and δ are the estimates of β and δ , respectively. An estimate of non-procedural costs

 (NPC_i) is then obtained for each subject i by adding subject specific variable costs to the average cost of an uncomplicated subject

Confidential and Proprietary Do not distribute or reproduce without prior permission of Abbott Vascular Inc.

$$\hat{NPC}_i = \overline{UHC} + \hat{Q}_i.$$

We will then calculate total hospital cost by adding the resource-based procedure costs to the estimated non-procedural costs, i.e.

$$TC_i = NPC_i + PC_i$$
.

Finally, in order to preserve subject variability in the cost data, residuals drawn from the step (1) regression will be added to the expected values. The approach outlined above will be used to calculate the cost of each index hospitalization as well as any subsequent hospitalizations during which a coronary revascularization procedure is performed.

For all other cardiovascular hospitalizations, data on principal and secondary diagnoses and any major procedures performed will be used to assign a DRG to the hospitalization. This mapping procedure will be performed in a blinded fashion by the MAHI HETA group working in conjunction with a trained Medicare coder. For each subsequent hospitalization, costs will be assigned based on the average cost for the relevant DRG based on MedPAR data. As noted previously, prior to performing the economic analysis, all rehospitalizations will be reviewed by an independent review committee (blinded to treatment group) to determine those hospitalizations that are unrelated to cardiovascular disease or its direct complications that will be excluded from the analysis.

As a sensitivity analysis, a more direct, resource-based approach to estimating non-procedural hospital costs will be considered. For this approach, either the MEDPAR database or a large, single-center database (e.g., Mid America Heart Institute) will be used to develop a regression model for non-procedural hospital costs based on subject characteristics, length of stay (LOS) elements (ICU, non-ICU), as well as specific procedures and in-hospital complications. The regression coefficients from the associated models will then be used to estimate non-procedural hospitalization costs based on the observed resource utilization data from the EXCEL population. All other costs (e.g., procedural costs, cardiovascular hospitalizations without revascularization procedures) will be calculated in the identical fashion to the "event-based" approach described previously.

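### Step 2 of the event-based hospital costing names only a PCI source for mean procedure cost; applied literally to CABG, it mis-costs each CABG admission by the CABG–PCI procedure-cost gap

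*Protocol*

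**What the plan says.** Protocol 17.4.2 makes the event-based approach the primary method for non-procedural hospital costs and builds it in three steps.

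- **Step 1** regresses total admission cost in MedPAR on complications and baseline characteristics. "This model will be estimated separately for each procedure type", so PCI and CABG each have their own intercept. On the intercept the section says: "A represents the sum of procedural costs and any other costs for an uncomplicated hospitalization".
- **Step 2** obtains the non-procedural cost of an uncomplicated stay. The instruction is to "subtract an estimate of mean procedure costs" from the estimate of A. The sentence on where that mean comes from names one kind of source, the "REPLACE-2 trial (14) or a comparable multicenter registry or trial that reflects contemporary PCI practice in a broad, relatively unselected subject population".
- **Step 3** adds the patient-specific terms, and then: "We will then calculate total hospital cost by adding the resource-based procedure costs to the estimated non-procedural costs".

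On scope, the section says: "The approach outlined above will be used to calculate the cost of each index hospitalization as well as any subsequent hospitalizations" that include a coronary revascularization. CABG admissions are therefore covered.

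Section 17.4.1 describes bottom-up costing of the catheterization laboratory and adds: "Similar methods will be applied to estimate the procedural cost of CABG". It does not mention step 2.

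**The concern.** The procedure cost taken out in step 2 and the one put back in step 3 should be for the same procedure. For PCI they are. For CABG, the intercept contains a CABG procedure cost and step 3 adds a CABG procedure cost, but the stated source for the amount removed in between reflects PCI practice. The two CABG terms then do not cancel.

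At stake are the primary cost endpoint (three-year cardiovascular cost, 17.5.3) and the cost-effectiveness ratio built on it (17.5.4). The error would be a fixed amount per CABG admission. CABG is the index procedure of one arm, so the error falls mainly on that arm.

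**Working it through.** The documents state no dollar figure for this step, so there is nothing to reproduce. The check is algebra on the protocol's equations, followed by a simulation with assumed costs.

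**Inputs (all from 17.4.2)**

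- `A_CABG`: intercept of the CABG model = mean CABG procedure cost `m_CABG` + mean other cost of an uncomplicated CABG stay.
- `m_PCI`: the external mean procedure cost from the named PCI source.
- `Q_i`: the patient's complication and baseline terms.
- `PC_i`: the patient's own bottom-up procedure cost.

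**Per admission**

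- Consistent with the protocol's identity (mean total = mean uncomplicated non-procedural + mean procedural, within one model): `TC_i = (A_CABG − m_CABG) + Q_i + PC_i`
- With the only named source: `TC_i = (A_CABG − m_PCI) + Q_i + PC_i`
- Second minus first: `g = m_CABG − m_PCI`, the same for every CABG admission.

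The residuals added back at the end of step 3 preserve variability and do not change this expectation.

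**Simulation.** 200,000 CABG admissions per row, least-squares fit. All costs are assumptions for illustration; none comes from the documents.

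| Assumed CABG / PCI procedure mean ($) | Gap g ($) | True mean total ($) | Mean total, CABG mean removed ($) | Mean total, PCI mean removed ($) | Error with PCI mean ($) |
|---|---|---|---|---|---|
| 8,000 / 6,000 | +2,000 | 24,194.3 | 24,195.1 | 26,195.1 | +2,000.8 |
| 12,000 / 6,000 | +6,000 | 28,210.6 | 28,212.8 | 34,212.8 | +6,002.2 |
| 8,000 / 8,000 | 0 | 24,217.7 | 24,217.5 | 24,217.5 | −0.3 |
| 7,000 / 9,000 | −2,000 | 23,216.8 | 23,216.1 | 21,216.1 | −2,000.7 |

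The error equals the gap in sign and size. With the CABG mean removed it is under $3, which is simulation noise.

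**Between arms.** Let `n_C` and `n_P` be the mean numbers of CABG admissions per subject in the CABG and PCI arms. Ignoring discounting and the cap at the 99th percentile, the shift in the cost difference (CABG minus PCI) is

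`g × (n_C − n_P)`.

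PCI-arm patients who later have CABG carry the same error. CABG-arm patients who never have CABG carry none under intention to treat. If `n_C − n_P` is assumed to lie between 0.8 and 1, each $1,000 of gap moves the arm difference by 1,000 × 0.8 = $800 to 1,000 × 1 = $1,000.

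**Would the plan detect it?** The bootstrap in 17.5.3 resamples patients, and the same constant sits in every replicate's CABG admissions. The interval is therefore centred on the shifted value. The resource-based approach models non-procedural cost directly and needs no subtraction. The opening of 17.4.2 lists it as the secondary approach, but the paragraph that describes it only says it will be considered. Any disagreement between the two methods could also be put down to length of stay differing between countries, which 17.4.2 gives as the reason for preferring the event-based method.

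**The case against.** The strongest reply is that this is an incomplete sentence and not a planned error. Nothing in 17.4.2 expressly says that a PCI mean is to be subtracted from the CABG intercept. The protocol's own identity, read within the CABG model, makes the mean procedure cost a CABG cost. The analysts will hold bottom-up CABG costs under 17.4.1. The section says the approach matches the one used in SYNTAX, itself a PCI-versus-CABG comparison, whose inputs are not in these documents. Section 17 calls these general plans, SAP 2.3.4 places the economic analyses elsewhere, and 17.6 allows the economics group to change the plan with executive review.

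Much of this stands, and it limits the claim. A reader might infer that the trial will certainly mis-cost CABG; the documents show only that the one stated sourcing rule would do so if followed. But that rule is worded for the whole step, conflicts with the identity it serves, and is not corrected by 17.4.1, which is never linked to step 2. Freedom to amend later does not settle the matter, because the input could then be chosen with arm-level results in view.

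Three stronger inferences also fail:

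- **That CABG is over-costed.** This needs a CABG procedure mean above the PCI mean, and neither is given. The SYNTAX difference of about $6,000 in initial revascularization cost (section 2.5) is not stated to be procedure cost alone.
- **That the arm difference moves dollar for dollar.** This holds only if `n_C − n_P` equals 1.
- **That the error can be scaled against the $6,300 left main cost difference or the 0.03 QALY difference in section 2.5.** Those are one-year SYNTAX results. EXCEL's cost endpoint is at three years and its primary cost-effectiveness horizon is lifetime (9.3.3). If the SYNTAX method was the same, its figures may already contain the same shift.

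**Conclusion.** Step 2 is wrong as written for CABG: its only stated source for the mean procedure cost is a PCI source, while the intercept it corrects is procedure-specific. Applied literally, each CABG admission is mis-costed by mean CABG minus mean PCI procedure cost, and the arm difference shifts by that gap times the between-arm difference in CABG admissions per subject. Sign and dollar size cannot be found from the documents, and zero is possible.

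The conclusion assumes that the named source is used for both models and that bottom-up patient costs are on the same scale as the procedure cost inside the MedPAR intercept. For PCI, cancellation likewise requires the external PCI mean to match the one embedded in the PCI intercept.

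The scope is narrow: event-based costing of revascularization admissions in the economic sub-study. Admissions costed by DRG, the resource-based analysis and all clinical endpoints and hypothesis tests are untouched. It should still be corrected, because it sits in the primary costing method and is cheap to remove.

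**What to change.** In step 2 of 17.4.2, state that the mean procedure cost is specific to the procedure type of the model. Use the PCI trial or registry source for the PCI model only. For the CABG model, use a mean CABG procedural cost from a CABG source or from the bottom-up CABG costing in 17.4.1. Express each mean in the same dollar year as the MedPAR extract.

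The change takes about one sentence and one extra external cost input. It needs no further patient data.

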17.4.3. Other costs

For all hospitalizations associated with coronary revascularization procedures, physician costs will be estimated on the basis of standard procedural codes and the Medicare Fee Schedule. For all other hospitalizations, physician costs will be estimated as a percentage of hospital costs according to DRG and corresponding Medicare physician cost to hospital cost ratio.^{167,168} Costs for outpatient medical care resource utilization (office visits, ER visits, non-protocol diagnostic tests) will be applied according to the Medicare Fee Schedule, and skilled nursing facility and rehabilitation stays will be estimated using Medicare reimbursement rates. Medication costs will be estimated based on an average per subject per month cost for each medication class. The mean cost for each class of medication will be based on an analysis of managed care pharmacy claims for subjects with coronary artery disease.

17.5. Analytic Plan

17.5.1. Quality of Life Endpoints

Since quality of life is a multidimensional construct for which different subjects may have different individual preferences, no specific scale will be considered as the "primary" QoL endpoint of the EXCEL trial. Rather, the goal of the study will be to describe any differences in the various quality of life scales over the time-frame of the trial. To limit any "false positive" results due to the large number of scales and timepoints evaluated, all QoL analyses will be performed using a p-value of <0.01 as an indicator of statistical significance.

For each of the quality of life measures in this study, data analysis will proceed in two stages. First, a simple descriptive and comparative analyses of cross-sectional data by intention-to-treat will be performed. For these cross-sectional analyses, comparisons will be performed at each follow-up timepoint using analysis of covariance to adjust for any baseline differences, including baseline score, between the treatment groups. Second, in order to account for missing data, longitudinal random coefficient growth curve models will be used to examine the effect of CABG versus PCI over time on each health status/QoL outcome. These models readily accommodate linear and nonlinear changes over time, as well as missing data patterns commonly seen in longitudinal studies. These analyses will incorporate all available QoL scores including those for subjects who die, withdraw from the study, or are lost to follow-up. Variables included in the longitudinal models for each outcome will include treatment (according to intention to treat), follow-up time (using linear, quadratic, and cubic terms), and interactions between treatment and each time term. In addition, these analyses will adjust for any baseline sociodemographic and clinical factors that differ between the two groups.

A particular challenge in the analysis of quality of life data relates to the problem of missing data (due to death, incapacity, subject refusal, or loss to follow-up). The proposed analytic strategy assumes that measurements are missing at random, however it is possible that subjects with impaired quality of life may be less likely to complete the interview. The sensitivity of the results to a variety of alternative assumptions regarding the relationship between quality of life and the likelihood of completing the QoL questionnaires will be examined. Potential approaches will include imputing missing values with the natural "worst case" score for each of the quality of life endpoints and application of multiple imputation techniques.¹⁶⁹

